#### **308 5.6 Calculation of Insulin Metrics**

- Insulin details (like units and numbers of boluses and basal) over the previous 7 days will be captured on a CRF at randomization, 1, 8, 13 weeks, or at the early termination in both arms. In the AID arm, detailed insulin data will be available from the Tandem pump download.
- CRF data in the Control arm and CRF data (baseline) and Tandem pump data (follow-up) in the AID arm will be used for the calculation of these metrics.
- In the Control group, the CRF data completed at 1 week prior to randomization will serve as baseline; while the CRF data completed at 13 weeks (or at early termination) will serve as the follow-up data.
- In the AID group, Tandem pump data from the week prior to randomization and the week prior to the 13 weeks visit will be used to define and calculate baseline and follow up metrics. If the 13 weeks visit occurs after 91 days from randomization, then the data from days 84 to 90 will be used. If a participant terminates the study earlier than 13 weeks, then the last 7 days in the study will be used to define follow-up.
- For the AID group, will include only days with complete insulin data and at least 5 such days are required for the metrics to be calculated. If there are not 5 such days, the participants will not be included in the insulin analyses. Since Tandem pump automatically generates a basal record every hour, at least 20 such hourly records are required for a day to be considered complete with insulin data and to be counted towards the minimum of 5 days.
  - Weight at baseline and at 13 weeks will be used to calculate insulin units/kg metrics.
- 327 328 329

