### 336 **5.8 Analysis Windows**

Analysis windows apply to the following outcomes measured at 13-week final visit:

- HbA1c
- Insulin (Control group only; see Section 5.6)
- Weight
  - Questionnaires
- 341 342

To be included in the corresponding analyses, these data must be collected between days 61 and 121 from the randomization. The target date is 91 days from the randomization.

345

This does not apply to the CGM or insulin metrics (AID group only) which are calculated as described above in Section 5.6.

348 349

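### SAP 5.6 contradicts itself on AID baseline insulin, drops AID participants who come off the pump but stay in the study, and with SAP 5.8 treats early exits differently by arm

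*SAP*

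**What the plan says.** **Baseline.** SAP 5.6 says that insulin details for the previous 7 days are "captured on a CRF at randomization, 1, 8, 13 weeks, or at the early termination in both arms". Its second bullet assigns sources: "CRF data in the Control arm and CRF data (baseline) and Tandem pump data (follow-up) in the AID arm will be used". Its third bullet says that in the Control group "the CRF data completed at 1 week prior to randomization will serve as baseline", although the list of CRF time points has no such visit. Its fourth bullet says that baseline and follow-up are defined by pump data: "In the AID group, Tandem pump data from the week prior to randomization and the week prior to the 13 weeks visit".

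**Minimum data, AID only.** A pump day is complete with at least 20 hourly basal records, and 5 complete days are needed. "If there are not 5 such days, the participants will not be included in the insulin analyses". Control has no such rule.

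**Early exit.** For Control, SAP 5.6 accepts the CRF from week 13 or from early termination. For an AID participant who leaves early, "then the last 7 days in the study will be used to define follow-up". SAP 5.8 lists Control insulin among the outcomes for which "these data must be collected between days 61 and 121" from randomisation, and exempts AID insulin.

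**Principles and use.** SAP 6.1 analyses participants as randomised regardless of system use, and SAP 6.2 keeps partial data by maximum likelihood. Protocol 5.5 asks AID participants who stop the system to stay to week 13, and 9.6.1 encourages the same. SAP 8.6 plans a formal comparison of 13-week insulin between arms, adjusted for baseline.

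**The concern.** The two baseline bullets cannot both be followed. The two follow-up rules matter more, because each decides who enters the comparison by something that happens after randomisation, and each does so differently by arm.

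The 5-day rule removes AID participants because they stopped the device. If their insulin use differs from that of people still on the pump, the comparison no longer describes the randomised groups. The exit rule lets insulin from early in follow-up stand as 13-week insulin in one arm only. Early AID insulin need not resemble week 13: Protocol 4.6.1.1 starts injection users on the pump at a total daily dose reduced by about 20%.

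Protocol 1.5.2 mentions lower insulin use with pumps as a possible benefit, so this comparison will be read.

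**Working it through.** **1. Is there a plan figure to reproduce?** None for insulin. The only power statement concerns HbA1c. With residual SD = sqrt(1 - 0.3^2) = 0.954 and 200 versus 100 completers, differences of 0.38, 0.35 and 0.33 give 90.2%, 85.0% and 80.6% power, against 90%, 85% and 80% stated. It reproduces, and nothing below changes it.

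**2. Can the pump bullet be carried out for baseline?**
- Protocol 4.6: the study pump starts on the randomisation day or up to 7 days later.
- Protocol 3.1: participants keep their own pump or injections during run-in.
- Protocol 2.2.2 excludes current hybrid closed-loop users, and Protocol 1.2 describes Control-IQ as such a system.
- Protocol 1.5.1.11: downloads from a personal pump are collected.

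A Tandem log for the week before randomisation can therefore exist only for someone with a personal Tandem pump not used as a hybrid closed-loop system. The CRF bullet works for everyone.

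**3. Who enters the insulin comparison?**

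| Participant | AID | Control |
|---|---|---|
| Stays to week 13 on assigned treatment | Counted, given 5 complete pump days | Counted from CRF |
| Leaves the study at day 40 while on the pump | Counted: last 7 days, no day limit | Not counted: CRF falls before day 61 |
| Leaves after day 60 | Counted | Counted: CRF falls in the window |
| Comes off the pump at day 40, stays to week 13 | Excluded: no pump days in the final week | No counterpart |

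Rows 2 and 4 show the oddity within AID: a participant who leaves altogether at day 40 is kept, while one who stops the pump on the same day and stays, as the protocol asks, is dropped.

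**4. How many could be affected?** The plan randomises 330 at 2:1, so 220 and 110. It allows 10% dropout per group: 22 AID and 11 Control. It gives no pump-stopping rate and no exit timing, so the counts below are illustrations.

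- *Pump stoppers who stay* (assumed 2%, 5%, 10% of 220): 4.4, 11, 22.
- *AID exits before day 61 that count*, if exits are even over 91 days (assumption) and at least 5 complete pump days exist: 22 x 55/91 = 13.3 with the pump started on day 0; 22 x 48/91 = 11.6 with the start deferred 7 days. This also assumes that the final week is uploaded.
- *Control exits before day 61*, same assumption: 11 x 60/91 = 7.3. From day 28, when Protocol 5.5 adds the 13-week procedures to the exit visit: 11 x 33/91 = 4.0. None counts under SAP 5.8.
- *Range*: 0 if all exits come after day 60; up to about 22 AID counted against 0 of 11 Control if all come before day 61.

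The stopper and exit counts must not be added. The plan uses the 10% to go from 220 randomised to 200 using the system, so the allowance may already include stoppers.

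**5. Which endpoints?** SAP 5.2 lists total, bolus and basal insulin, each in units and units/kg (6), plus percent basal (1): 7 metrics. Protocol 11.4.3 calls this set of endpoints exploratory. SAP 16 puts insulin in one false-discovery-rate group with weight, lipids, creatinine and blood pressure.

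**The case against.** **The baseline clash is a slip.** This stands. The second bullet labels its sources outright, and the fourth cannot be carried out for most people. A reader might infer that the fourth bullet, combined with the 5-day rule, removes every injection user: 0.25 x 220 = 55 if the 25% recruitment minimum is just met and balanced by arm. The documents do not support that as a realistic loss, because the labelled CRF baseline is available to all.

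**Not every stopper is lost.** This stands too. Someone who turns closed loop off but stays on the study pump still generates basal records and can have 5 complete days.

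**Minimum-data rules are normal here.** SAP 5.3 requires 168 hours of follow-up CGM data. But that rule covers the whole 13 weeks and both arms, and participants who stop the system are asked to keep wearing the CGM. The insulin rule applies to one arm and, in practice, depends on device use in one week.

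**SAP 5.6 accepts the Control early-termination CRF, so SAP 5.8 may not override it.** The sections can be read that way, and SAP 5.6 alone shows no asymmetry. But SAP 5.8 names Control insulin, states the window as a condition for inclusion and exempts only AID. The reading that respects both is that an early-termination CRF counts only from day 61.

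**Accepting early-termination data in both arms would also restore symmetry.** True, but it would let early insulin stand as 13-week insulin in both arms, while SAP 8.6 compares 13-week metrics.

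**Conclusion.** The baseline contradiction is real but needs only a wording correction; under the natural reading nobody is lost. The two follow-up rules are errors as written. One excludes AID participants who come off the study pump well before week 13 and stay in the study, against SAP 6.1 and 6.2. The other, from SAP 5.6 and 5.8 together, counts early exits in AID and not in Control.

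The number affected is unknown; the counts above rest on assumed stopping rates and even exit timing, and the exit effect could be 0. Only the 7 exploratory insulin metrics are touched.

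A reader might also infer that the units/kg metrics will rest on fewer AID participants than the units metrics, because SAP 5.8 puts a window on weight and SAP 5.6 says "Weight at baseline and at 13 weeks will be used to calculate insulin units/kg metrics". That holds only if the weight window also governs this denominator, which the SAP does not say.

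The point should be settled before analysis. The wording clash is certain; the size of the effect is not.

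**What to change.** 1. State that baseline insulin is the randomisation-visit CRF, covering the previous 7 days, in both arms. Remove the pre-randomisation pump source from the fourth bullet and align the third bullet with the listed CRF time points.
2. Limit the 5-complete-day rule to AID follow-up pump data. For AID participants without a qualifying pump week, use the 13-week insulin CRF. Cost: mixed data sources within AID for those few.
3. Apply the day 61 to 121 window to follow-up insulin in both arms. Treat earlier exits as missing follow-up, handled by the direct-likelihood model. Cost: some early AID data are not used as follow-up, and those values are assumed missing at random.

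These are changes to SAP wording, with no effect on sample size. They rely on SAP 5.6, which says the insulin CRF is collected in both arms at randomisation and week 13. The protocol's visit procedures (5.2.1) mention only total daily dose over the last week, and its randomisation procedures (4.2) list no insulin form, so confirm that the CRF holds the bolus and basal split.

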#### 330 5.7. Questionnaires

Participants are allowed to skip specific questionnaires or items within a questionnaire. The data might
therefore include some missing items. If applicable, questionnaires will be scored according to the
instructions given in the manual. If a total or a sub-scale score is calculated but no instructions exist,
then at least 75% of the items should be non-missing for the total or sub-scale score to be calculated.

335

338

339 340

### 336 **5.8 Analysis Windows**

Analysis windows apply to the following outcomes measured at 13-week final visit:

- HbA1c
- Insulin (Control group only; see Section 5.6)
- Weight
  - Questionnaires
- 341 342

To be included in the corresponding analyses, these data must be collected between days 61 and 121 from the randomization. The target date is 91 days from the randomization.

345

This does not apply to the CGM or insulin metrics (AID group only) which are calculated as described above in Section 5.6.

348 349

### 6. Description of Statistical Methods

- 350 351
- 352 6.1. General Approach:

- All analyses comparing the AID arm with Control arm will follow intention-to-treatment (ITT) 353 • approach, which means participants will be analyzed in the treatment arm assigned by 354 randomization regardless of the actual system use. All randomized participants with any data will 355 be included in the primary analysis and secondary analyses. 356 In the unlikely event that an enrolled participant is later found to be ineligible, the participant 357 • will be excluded from all analyses. 358 • All covariates obtained on a continuous scale will be entered into the models as continuous 359 variables unless it is determined that a variable does not have a linear relationship with the 360 outcome. In such a case, categorization and/or transformation will be explored. 361 All p-values will be two-sided. 362 • Standard residual diagnostics will be performed for all analyses. If values are highly skewed, 363 then a nonparametric or robust regression using M-estimation will be used instead for the 364 primary and secondary outcomes. Previous experience suggests that no transformation, 365 366 nonparametric, or M-estimation analyses will be necessary for HbA1c, mean glucose, % time in range 70-180 mg/dL, or % above 180 mg/dL. Other outcomes like % below 54 mg/dL will likely 367 be skewed with a need for a transformation, nonparametric, or M-estimation. 368 369 370 **6.2 Analysis Cohorts** 371 372 373 Primary and Secondary Analyses: All randomized participants with any data will be included in the primary and secondary analyses. 374 • Any partial data (i.e., missing baseline or follow-up) will be handled using the maximum likelihood 375 method (see Section 7 below). 376 377 • All participants with at least one meal challenge and with the minimum amount of CGM data during these periods – as defined above in Section 5.4 - will be included in the corresponding meal analysis. 378 Similar for participants with at least one scheduled exercise and the exercise analyses. 379 380 381 Per Protocol (PP) Analyses: Per-protocol analyses will be performed for primary outcome and secondary hierarchical outcomes (see 382 Section 8.2 below) only if >5% of participants will be excluded. All of the following criteria must be 383 met for a participant to be included in the per-protocol analyses. The criteria are as follows: 384 385 • 13-week visit completed,
- No major protocol deviations, and
- Device use: AID group closed loop mode active for at least 80% of the time over the 13-week
   period; control group CGM use for at least 80% of the time over the13-week visit period.
- 389
- 390 Safety Analyses:
- Safety outcomes will be reported for all enrolled participants, irrespective of whether the participant
   was randomized, or the study was completed.

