1371	 Insulin
1372	 Total daily insulin delivery
1373	 Percentage of insulin delivered as basal
1374	Weight change
1375	 Change in lipid levels
1376	Cardiovascular events
1377	• Patient-reported outcome (PRO) measures (see section 8.3)
1378	11.4.4 Safety Endpoints
1379	Severe hypoglycemia
1380	Diabetic ketoacidosis
1381	 Hyperosmolar hyperglycemic syndrome
1382	Other serious adverse events
1383	 Unanticipated adverse device effects
1384	• Hypoglycemia and prolonged hyperglycemia endpoints listed as effectiveness endpoints
1385	• Infusion set failures
1386	Other device malfunctions/device issues
1387	11.5 Analysis Datasets and Sensitivity Analyses
1388 1389 1390 1391	All analyses comparing the AID arm with Control arm will follow intention-to-treatment approach, which means participants will be analyzed in the treatment arm assigned by randomization regardless of actual system use. All randomized participants will be included in the primary analysis and secondary analyses of CGM metrics.
1392 1393	Safety outcomes will be reported for all enrolled participants, irrespective of whether the participant was randomized, or the study was completed.
1394	11.5.1 Per Protocol Analyses
1395 1396 1397	Per-protocol analyses will be performed for primary outcome and secondary hierarchical outcomes only if >5% of participants will be excluded. All of the following criteria must be met for a participant to be included in the per-protocol analyses. The criteria are as follows:
1398	• 13-week visit completed
1399	 No major protocol deviations

Device use: AID group - closed loop mode active for at least 80% of the time over the
 13-week period; control group - CGM use for at least 80% of the time over the
 visit period

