	2. Current use of systemic glucocorticoids or anticipated use of glucocorticoids during the RCT ( topical or inhaled -ie, non-systemic is acceptable ).					
	3. Current use of sulfonylurea or meglitinide medications					
	4. Current use of hydroxyurea					
	5. Tape allergy or skin condition that will preclude use of the study pump or CGM					
	6. Presence of a hemoglobinopathy or other condition that is expected to affect the measurement of HbA1c					
	
 
Pregnant (positive urine hCG), breast feeding, plan to become pregnant during the study period, or sexually active without use of accepted contraceptive measures
 
					
	8. Current participation in another diabetes-related interventional clinical trial					
	9. Anticipated change of residency or travel for more than 7 days at a time during the study that may, per investigator judgment, interfere with the completion of study visits, contacts, or procedures					
	10. Immediate family member (spouse, biological or legal guardian, child, sibling, parent) who is an investigative site personnel directly affiliated with this study or who is an employee of Tandem Diabetes Care, Inc.					
	Eligibility for Exercise Challenges					
	All participants will have a screening EKG or review of an EKG completed in the 12 months prior to screening.					
	To participate in the exercise challenge, a participant must not have a history of a cardiovascular event in the year prior to screening and/or EKG abnormalities associated with increased risk during exercise.					
Sample Size	A maximum of 450 individuals may be enrolled (consented for screening) in order to achieve the goal of 330 randomized participants.					
	This equates with a maximum of 220 using the AID system for 13 weeks and 110 using pre-study basal-bolus insulin delivery method plus the study CGM. Assuming 10% drop out rate in each group, there will be 200 using the system for 13 weeks.					
	Approximate Study Goals					
	- Minimum 25% MDI users					
	- Minimum 30% of a minority race or ethnicity					
	- Minimum 10% older than 50 years old					
	- Minimum 20% using an SGLT2 inhibitor,20% using a GLP-1 receptor agonist, and a minimum of 10% using both					

PARTICIPANT AREA	DESCRIPTION				

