# 2. Comparison with the Protocol

The author of this document confirms that this SAP is consistent with version 5.0 of the Protocol, exceptthe following:

- New formal analyses were added to compare the night following meal or exercise challenges with the previous 14 nights without any previous day challenge.
- 94 95

96 97

101

103 104

92

93

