#### 521 9. Safety Analyses

522

All enrolled participants will be included in the safety analyses and all of their post-randomization safety
events will be reported by the treatment group. Separately, any adverse events occurring between
screening and randomization will be reported.

All reportable adverse events will be tabulated by the treatment group. Details will be provided in a
listing of each event, including Medical Dictionary for Regulatory Activities (MedDRA) term and
MedDRA System Organ Class. Safety analyses for the RCT will include events occurring on or after
randomization until and including the 13-week visit or Day 98 from randomization, whichever occurs
first.

- 531 The safety metrics will include:
  - Severe hypoglycemia
- Diabetic ketoacidosis
- Hyperosmolar hyperglycemic syndrome
- Other serious adverse events
- Unanticipated adverse device effects
- Hypoglycemia and prolonged hyperglycemia endpoints listed as effectiveness endpoints
- Infusion set failures
- Other device malfunctions/device issues
- 540

- All safety metrics listed above will be tabulated by the treatment group. Formal statistical testing only will be performed for selected safety endpoints. For the following outcomes, mean  $\pm$  SD or summary statistics appropriate to the distribution will be tabulated by treatment group and formal statistical comparisons will be performed if there are enough events (at least 5 events combined between the two treatment groups):
- Number of SH events and SH event rate per 100 person-years
- Number of DKA events and DKA event rate per 100 person-years

- Number of hyperosmolar hyperglycemic syndrome events and rate per 100 person-years
  - Other serious adverse events

If enough events occur for the severe hypoglycemia and DKA outcomes and other serious adverse
events, the numbers of events will be compared between the two treatment groups during the RCT using
a robust Poisson regression as detailed in the SAP.

553

549

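### SAP 6.1 drops participants later found ineligible from every analysis, contradicting the all-randomised rule in SAP 6.1, SAP 6.2 and protocol 11.5, and SAP 2 does not declare it

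*SAP*

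**What the plan says.** The rule is the second bullet of SAP 6.1: "In the unlikely event that an enrolled participant is later found to be ineligible, the participant" "will be excluded from all analyses". The bullet before it adopts intention to treat and includes every randomised participant who has any data.

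Three other places define the sets, none with an eligibility exception:

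- SAP 6.2, efficacy: "All randomized participants with any data will be included in the primary and secondary analyses".
- Protocol 11.5, efficacy: "All randomized participants will be included in the primary analysis and secondary analyses of CGM metrics".
- Safety: SAP 6.2 has "Safety outcomes will be reported for all enrolled participants, irrespective of whether the participant" was randomised or completed the study, SAP 9 has "All enrolled participants will be included in the safety analyses", and protocol 11.9 includes all randomised participants.

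SAP 2 states that "this SAP is consistent with version 5.0 of the Protocol" apart from one listed item, the analyses of nights after challenges. Excluding ineligible participants is not listed.

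**The concern.** An analyst who meets one such case has two incompatible instructions for HbA1c and the nine hierarchical secondary endpoints.

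If the exclusion is followed, nothing limits when ineligibility may be found, who decides, what they know when deciding, or whether the fact existed before randomisation. Treatment is visible to participants and sites, and several criteria rest on investigator judgement. Inclusion criterion 12 is a belief that the participant can operate all study devices. Criterion 3 is a clinical diagnosis of type 2 diabetes on investigator assessment, while C-peptide and GAD antibodies are drawn only at the randomisation visit, so those results need not be known before allocation. A decision to reclassify someone could be made with arm and glucose data in view. Intention to treat exists to close that route.

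**Working it through.** **1. Can the texts be read together?** The one reading that removes the conflict is that the bullet concerns screen failures only. Protocol 2.1.1 defines enrolled as having signed consent, so the word covers people never randomised as well as those who were. SAP Table 1 says: "A maximum of 450 individuals may be enrolled (consented for screening) in order to achieve the goal of 330 randomized participants". At that ceiling, (450 − 330)/450 = 120/450 = 26.7% of consented people are not randomised. Some of these would be withdrawals or run-in failures rather than people found ineligible, but a group of that size does not fit an event called unlikely. The phrase about being found ineligible later also points to discovery after entry. The screen-failure reading is strained, and the wording does not impose it.

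**2. Is it declared?** SAP 2 lists one departure and this is not it. The SAP refers to protocol version 5.0, whereas the protocol supplied is version 8.0. The log entries for versions 6.0 to 8.0 mention no change to analysis sets, although the 6.0 entry includes an unspecified resolution of minor conflicts.

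**3. The plan's own power figure.** Inputs from SAP 4: SD 1.0, correlation 0.3 with baseline, two-sided 5%, 300 completers, allocated 2:1 as 200 and 100.

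- Residual SD = 1.0 × √(1 − 0.3²) = 0.954.
- Standard error = 0.954 × √(1/200 + 1/100) = 0.1168.
- Power for 0.38 = Φ(0.38/0.1168 − 1.96) = 0.902. The stated 90% is reproduced.
- Likewise 0.850 for a difference of 0.35 and 0.806 for 0.33, against the stated 85% and 80%.

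**4. Power if participants are removed (normal approximation, difference 0.38).**

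| AID / Control | Power |
|---|---|
| 200 / 100 | 0.902 |
| 198 / 100 | 0.901 |
| 198 / 99 | 0.899 |
| 190 / 100 | 0.897 |
| 190 / 95 | 0.887 |

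**5. Possible shift in the estimate.** Assumptions, none of them from the documents: k of 200 AID completers are removed, no controls, and those removed have 13-week HbA1c d points above the AID mean. The remaining AID mean falls by k × d/(200 − k).

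- d = 1.0, k = 2: 2/198 = 0.0101, which is 2.7% of 0.38.
- d = 1.0, k = 10: 10/190 = 0.0526, which is 13.9% of 0.38.
- If those removed are also 1.0 above at baseline, adjustment with slope 0.3 leaves d = 1.0 − 0.3 = 0.7. The shifts become 1.4/198 = 0.0071 and 7/190 = 0.0368.
- If k of 200 AID and k/2 of 100 controls are removed with the same d, both means move equally and the difference changes by 0.

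**6. Would the per-protocol analysis pick this up?** It runs only if more than 5% are excluded. 0.05 × 330 = 16.5, so at least 17. Two to ten ineligible participants are 0.6% to 3.0% of 330 and would not trigger it alone. At the planned 10% dropout (33 of 330) it would probably run anyway. But it also removes non-completers and people with low device use, so it would not isolate the effect of eligibility.

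**The case against.** The strongest reply is that this is a wording conflict with little practical effect. Criterion 12 records a belief held at entry, exclusion criteria apply at baseline, and eligibility is reaffirmed at the randomisation visit. Poor device use afterwards is therefore not retrospective ineligibility. Protocol 5.5 and 9.6.1 treat it as discontinuation of the device and ask the participant to stay in the study. A specific safety-set rule would normally prevail over a general bullet, so safety events need not be lost. SAP 11 already tabulates deviations by arm and accounts for participants in a flow chart. Version 5.0 of the protocol is not available. The illustrated shift assumes one-sided removal of participants a full SD above their arm mean.

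Much of this stands. Cases should be few, the criterion 12 example shows only that a route is open, the safety point is a conflict to reconcile and not a certain loss of events, and the non-declaration is inferred for version 5.0. None of it reconciles the bullet with the rules around it. The bullet itself does not restrict ineligibility to facts known at baseline, and the SAP 11 tabulations would record an exclusion without preventing it.

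**Conclusion.** The concern holds, and the SAP should be corrected. Excluding ineligible participants from all analyses contradicts the preceding bullet, SAP 6.2 and protocol 11.5. Read literally, it also conflicts with the safety sets in SAP 6.2, SAP 9 and protocol 11.9. SAP 2 does not declare it. That this is a departure from version 5.0 rests on the amendment log showing no later change to the analysis sets.

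The numerical effect is probably small. Under the one-sided assumptions above it reaches 0.053 HbA1c points at most, or 0.037 if baseline is raised by the same amount. It is zero if removals are proportionate and alike in both arms, and power for 0.38 stays between 0.887 and 0.901 against 0.902. The defect is an open-ended, unmasked exclusion rule applied after randomisation to the primary analysis.

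**What to change.** Delete the bullet in SAP 6.1 and replace it with three statements:

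1. Every randomised participant stays in the assigned arm for the primary, secondary and safety analyses, whatever is later learned about eligibility.
2. An eligibility failure counts as a major deviation for the per-protocol set only. Protocol 12.4 defines major deviations broadly and does not name this case.
3. Participants found ineligible after randomisation are listed by arm with the reason. Any analysis without them is a sensitivity analysis, based on facts from before randomisation and judged by someone masked to arm and outcome.

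The cost is a few sentences of SAP text, one listing and, if cases occur, one sensitivity analysis. There is no added data collection or participant burden.
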